PROTOCOL NARRATIVE

University of California, Irvine Institutional Review Board

Version: March 2006

HS#: 2006-5138 For IRB Office Use Only

Lead Researcher Name: [name]

Title: Evaluation of the Candela 1064nm Nd:YAG laser for Treatment of Cellulite and Tightening of Skin

Important: Please read the instructions before completing this protocol narrative.

NON-TECHNICAL SUMMARY

Provide a non-technical summary of the proposed research project that can be understood by IRB members with varied research backgrounds, non-scientists and community members. The summary should include a brief statement of the purpose of the research and related theory/data supporting the intent of the study and a brief description of the procedure(s) involving human subjects. *This summary should not exceed more than ½ a page*.

At present, there are no proven effective means for managing cellulite. There are two devices that have received FDA clearance for "temporary reduction in the appearance of cellulite". One is a mechanical massage machine (Endermologie, LPG, Fort Lauderdale, FL) under 510(k) K990445 and the other is the Velasmooth (Syneron Medical Ltd. Israel) under 510(k) K050397.

Non-ablative laser and light treatments are becoming an increasingly popular procedure. Non-ablative treatments have been shown to improve rhytides, pilosebaceous changes, pigmentary skin alterations and vascular lesions including facial telangiectasias and diffuse redness and are attractive to physicians and subjects because of minimal or no healing time, reducing subject inconvenience and risk.

It is our hypothesis that creating deep fibrosis in the skin will improve the appearance of cellulite. The laser used in this study will allow deep tissue heating, while using a cooling device to protect the outer layers from damage.

Approved by IRB on: 05/08/2009 HS# 2006-5138 Void After: 05/07/2010

IRB USE ONLY - DO NOT ALTER THIS FOOTER

e-CPA# 5126 1 of 20

SECTION 1: PURPOSE AND BACKGROUND OF THE RESEARCH

- 1. Describe the **purpose of the research** project and state the overall objectives, specific aims, hypotheses (or research question) and rationale for performing the study.
- 2. Provide the **relevant background information** on the aims/hypotheses (or research question) to be tested and the procedures/products/techniques under investigation.
- 3. Include a description of the predictor and outcome variables, as appropriate.

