- 4. Include a critical evaluation of existing knowledge, and specifically identify the information gaps that the project intends to address.
- 5. Describe previous research with animals and/or humans that provides a basis for the proposed research. Include references/citations, as applicable.

There are numerous therapies that have been advertised for the treatment of cellulite, but there is little scientific evidence that any of these treatments are beneficial. In fact, much of this evidence is subjective or based upon patient self-assessment. The objective of this investigation is to evaluate safety and effectiveness of a non-ablative treatment for cellulite in conjunction with skin tightening by increasing dermatofibrosis of the reticular dermis using the Candela GentleYAG laser.

Study outcome will be assessed as follows:

A panel of three independent, blinded individuals experienced in dermatological cosmetic therapy will determine percent improvement in cellulite appearance by comparing photographs taken at the pretreatment visit to those from the 1, 3 and 6 month follow-up visits. Each evaluator will be ask to compare the treated and non-treated areas on a blinded basis and then will rate improvement on the scale 0 to 4, as described below.

% Improvement Description		core
0%	No improvement	0
1-25%	Slight improvement	1
26-50%	Moderate improvement	2
51-75%	Significant improvement	3
76-100%	Complete improvement	4

The difference scores between the treated and the untreated sides will be used to measure treatment efficacy.

The investigator's assessments during follow-up visits will be tabulated and analyzed with basic descriptive statistical methods.

Ultrasound analysis, skin elasticity measurements and non-invasive optical measurements may also be performed prior to treatment and at the 1, 3 and 6 month follow-up visits to determine any changes in skin thickness.

Safety will be assessed by clinical evaluation of purpura, edema, erythema, hyperpigmentation, hypopigmentation, blistering and scarring. Assessments will be performed by the investigator using the following scale:

0 = absence 1 = mild 2 = moderate 3 = severe

SECTION 2: ROLES AND EXPERTISE OF THE STUDY TEAM

List all study team members below.

- Describe their specific role and responsibility on the study in the text box provided.
- 2. **Faculty Sponsors** list as Co-Researchers and describe their role on the project; include oversight responsibilities for the research study.

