This is an open label trial. Treatment will be conducted on either the left or right knee, thigh, arm, or ½ the abdomen, depending upon which area has the most cellulite or skin laxity. The contra-lateral side will not be treated and will serve as a control. A comparison of baseline photographs (prior to treatment) to photographs taken 1, 3 and 6 months after the completion of treatment will be conducted. Photographic equipment and the protocol for photography will be consistent at each visit. Ultrasound may be taken at baseline and at the follow-up visits to evaluate flatness of cellulite and dermal fibrosis or enlargement of the reticular dermis. Non-invasive light measurements may also be taken at baseline and follow-up visits. These do not hurt or pose a risk to the subjects and are similar to shining a flashlight on the skin and measuring the light. The area treated will be measured with a tape measure, weight/height will be recorded and the Body Mass Index (BMI) will be calculated at baseline and follow-up visits. In addition, skin elasticity may be measured at the treatment areas at baseline and follow-up visits. The photographs, ultrasound and measurements will be taken using consistent procedures at each visit by viewing the baseline photograph and using landmarks such as freckles and birthmarks.

The laser system to be used in this clinical study, Candela GentleYAG, a 1064 nm Nd:YAG laser is a commercially available laser and has been cleared by FDA under K022923, K022951, K023193 and K033172.

The Candela GentleYAG is cleared for removal of unwanted hair, for stable long term or permanent hair reduction and for treatment of pseudofolliculitis barbae, and is indicated on all skin types Fitzpatrick I-VI including tanned skin. The GentleYAG is cleared for treatment of vascular lesions such as port wine stain birthmarks, telangiectasia, rosacea, and leg and spider veins, and is cleared for treatment of benign pigmented lesions such as lentigos (age spots), café au lait birthmarks, and tattoos. The laser is also indicated for treatment of red pigmentation in scars with vascularity, and for treatment of wrinkles.

The Candela DCD produces a brief, timed spray of cryogenic fluid that evaporates from the skin surface and cools the epidermis, prior to each laser pulse. The DCD has been cleared by the FDA for minimizing pain and cooling the epidermis during laser treatment (K953412). The DCD is part of the Candela GentleYAG laser system.

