Treatment Procedure

The following table provides a summary of the required study visits, the procedures and assessments to be performed at each visit.

Assessments/ Procedures	Pre- Tx	Tx 1	Follow-up 1 month	Follow-up 3 months
Informed Consent	X			
History	X			
Inclusion/ Exclusion Criteria	X			
Subject No. Assignment Randomization	X			
Photography	X	X	X	X
Ultrasound/skin elasticity assessments (optional)	X	X	X	X
Non-invasive light measurements	X	X	X	X
Measurement (average of 3) / Weight	X		X	X
Laser treatments		X		
Assessments of side effects		X	X	X
Post-treatment care instructions		X		
Assessment			X	X
Subject Satisfaction survey			X	X

Pre-Treatment Procedure

- 1. Subjects will be recruited at the investigational site.
- 2. Prior to any screening assessments, informed consent will be obtained. When the subject fully understands the possible benefits and risks of the study, the subject will be asked to sign and date the informed consent form. The investigator will then sign and date the form. The subject will be given a copy of the completed consent form.
- 3. A detailed medical history will be obtained.
- 4. The subject will undergo a standard exam to determine if they meet the study criteria.
- 5. Skin type will be recorded using the Fitzpatrick classification of phototype.
- 6. Tape measurements of the treated area, height, and weight will be recorded.
- 7. The presence and severity of cellulite will be noted using the following 2 methods:

Nurnberger-Muller Scale:

- Stage 0: No dimpling. Pinch test "folds and furrows", no mattress like appearance.
- Stage 1: No dimpling. Pinch test reveals mattress like appearance.
- Stage 2: Dimpling spontaneously standing.

Stage 3: Dimpling spontaneously standing and lying down.

Texture Scale:

Hard or Solid: Pinch test "firm folds and furrows" mattress-like appearance. Adherent to deep planes. Not modified with lying versus standing position.

Soft or Flaccid: Pinch test "spongy and floating folds and furrows", mattress-like appearance. No adherence to deep planes. Not painful, flaccid. "Orange peel skin" appears spontaneously.

Edematous: Doughy consistency. Dimpling Spontaneously. Pain and cramps. Signs of venous and lymphatic insufficiency "legs in boot/column".

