- 8. The pre-treatment photographs will be obtained using the Canfield Monostand device. This device will keep the ambient lighting, background, camera settings exactly the same for each scheduled photograph during the study. Photographs will be of the treated and control areas.
- 9. Optional: Imaging of skin via a non-invasive high frequency ultrasound imaging device may be performed
- 10. Optional: Measurement of skin elasticity using non-invasive instrumentation may be performed.
- 11. Just prior to treatment, the subjects will be assigned a study subject number. These numbers will be assigned consecutively.

Laser Treatment:

[figure not shown]
One laser treatment will be performed, and the procedure will be as follows:

- 1. The treatment area will be photographed prior to the treatment. Emphasis will be placed on keeping the ambient lighting, background, camera settings exactly the same for each scheduled photograph during the study.
- 2. Tape measurement and weight will be recorded.
- 3. The treatment area will be comprised of the arm (circumferential upper arm area), knee (approximately 10cm circumferentially around the patellar bone), entire thigh (from the upper lateral areas of the thighs inner to outer area excluding hips moving downwards until just above the knee), or abdomen (from the costal margin to just superior to the pelvic bone).
- 4. Topical anesthetic may be applied to the skin according to the manufacturer's instructions if the subject requires it or if the doctors feels the subject might not tolerate the treatment with out the use of topical anesthetic
- 5. Starting with the selected diameter spot size handpiece, test spots may be conducted with the laser at a low fluence until the optimum fluence is achieved (prior to intolerable discomfort or a reaction of mild redness or edema is visible).
- 6. Laser treatment will include up to six (6) consecutive passes of the laser over the treatment area. The treatment parameters are noted in the following table.

Parameter	Parameter Value Range		
Spot size diameter:	10-22 mm		
Wavelength	1064 nm		
Fluence:	10-50 J/cm ²		
Laser pulse duration:	20-50 ms		
Rep. rate:	Up to 2 Hz		
DCD cooling	0-50ms		

Immediate Post-Treatment Procedure

1. Immediately after treatment the subject will be asked to rate the pain on a 0-10 (none to worst).

3. The subject will be instructed on post-treatment care.

Long Term Follow-Up Procedure

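### A compliant treatment can skip the test spot and use no cooling at any permitted fluence, although the protocol says that cooling protects the outer skin

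*Protocol*

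**What the plan says.** Three places in the Protocol bear on this point.

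- **Laser Treatment, item 5.** On setting the fluence, it says that "test spots may be conducted with the laser at a low fluence until the optimum fluence is achieved", followed by a bracket: "prior to intolerable discomfort or a reaction of mild redness or edema is visible".
- **Laser Treatment, item 6.** Up to six consecutive passes are allowed, within a table of separate ranges. Fluence is 10-50 J/cm², pulse duration 20-50 ms and repetition rate up to 2 Hz. The cooling entry reads "DCD cooling 0-50ms".
- **Non-Technical Summary.** The laser is said to heat deep tissue "while using a cooling device to protect the outer layers from damage".

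The device description ahead of the Treatment Procedure says that the spray "cools the epidermis, prior to each laser pulse". It adds: "The DCD has been cleared by the FDA for minimizing pain and cooling the epidermis during laser treatment".

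Section 1 states: "Safety will be assessed by clinical evaluation of purpura, edema, erythema, hyperpigmentation, hypopigmentation, blistering and scarring". These are graded from 0 (absence) to 3 (severe). The visit table has a row for "Assessments of side effects" that is marked at the treatment visit as well as at follow-up.

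**The concern.** The plan presents cooling as what protects the surface while the deep tissue is heated, and the test spot as the way to find a tolerable fluence. Neither is required. An operator may go straight to a chosen fluence, with the spray off, and still be within protocol.

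Section 7B lists blistering, pigment change and scarring among the risks and says that skin changes may be permanent. This is a cosmetic indication treated on one side of the body, so the tolerance for lasting skin injury is low. Safety is also one of the two stated objectives. If subjects differ in whether they were cooled and whether they were tested first, side-effect counts from 24 completers will be hard to attribute to a defined procedure.

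**Working it through.** No formula applies and the plan gives no figure to reproduce. The check is a side-by-side reading.

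1. **Is the test spot required?** No. The verb in item 5 is permissive. The starting fluence is called low without a number, and the optimum is not defined by a number. No other text shown sets an individual subject's fluence within 10-50 J/cm².

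2. **Is cooling required?** Not by the table. Its lower bound is 0 ms, which on the natural reading (spray duration) means no spray. The table does not say whether the entry is spray duration or delay. Duration is assumed here because the device description calls it a timed spray. Fluence and cooling are separate rows, with no rule tying a minimum spray to fluence, skin type, body site or spot size. So 50 J/cm² with 0 ms, for up to six passes, is a permitted combination.

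3. **Does that agree with the rationale?** No. The Non-Technical Summary says of the laser used in this study that a cooling device protects the outer layers. A treatment at 0 ms does not have that protection.

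4. **Does another section supply the missing safeguard?** Section 7B answers the form's question on preventing and minimizing risk with two items: the team's experience, and bleaching cream if hyperpigmentation occurs. The second acts after the event. Neither sets a test-spot, fluence or cooling rule.

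5. **Who is exposed?** Section 4B, inclusion criterion 4, admits phototypes I-IV. The rationale in item 3 of the same section speaks of enrolling I-III, because types IV and V had more pain and were more likely to develop dyspigmentation in previous 1064 nm studies. Under the eligibility list as written, type IV subjects can enter and be treated without either safeguard.

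6. **Where does escalation stop?** The bracket in item 5 can be read in two ways. If its opening words govern both phrases, mild redness or edema is a limit to stay below. If they govern only the discomfort, a visible reaction is the sign that the optimum has been reached. Both readings stop escalation at about the same test step. They differ on whether treatment is given at that step or just below it. Because erythema and edema are graded safety outcomes and side effects are assessed on the treatment day, the protocol should say which is meant.

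**The case against.** The best case for the plan is that operator latitude is deliberate. This is a single-site pilot with a commercially available, FDA-cleared laser, used by an experienced team. Eligibility already excludes phototypes V-VI, known photosensitivity, and a personal or family history of keloids or scarring. A table of ranges need not mean that every corner is intended, and no text says that uncooled pulses at 50 J/cm² injure skin. Part of the text before the device description, and a figure under the Laser Treatment heading, were not available, so a dosing rule there cannot be ruled out.

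Much of this stands. It limits what can be claimed about harm, and it supports keeping the fluence range. It does not remove the conflict between the summary's statement about cooling and a table that allows none. Nor does experience tell an operator whether a test spot is expected.

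A reader might infer more than the documents support:

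- **That the bracket in item 5 is itself a serious safety flaw.** On either reading escalation stops at or just before the first mild reaction, so this is a wording clarification.
- **That the fluence range, or one grade on the 0-3 scale, measures the defect.** The range survives any sensible fix, and nothing applies that scale to test spots.
- **That the device description is wrong.** It says how the spray works and sets no study rule. Only the summary's sentence conflicts with the table.
- **That treatment must stay below visible redness, or be withheld from subjects who react at the lowest fluence.** These are clinical trade-offs against the deep heating that the hypothesis needs. The protocol gives no basis for either threshold.

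**Conclusion.** The point holds as a cheap safety improvement. In the text shown, both the test spot and the cooling can be omitted at any fluence up to 50 J/cm², and the second omission contradicts the Non-Technical Summary. It is a matter of treatment delivery and safety. It does not affect the efficacy comparison or its analysis.

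The size of the harm cannot be computed, because the protocol gives neither an injury threshold for uncooled pulses nor any rate for the listed risks. The conclusion assumes that the cooling entry is spray duration and that the text not available contains no overriding rule.

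**What to change.** 1. **Item 5.** Reword along these lines: *Test spots will be done in every subject before treatment, starting at a low fluence and using the DCD setting planned for treatment.* Then state whether first visible mild redness or edema is the stopping limit or the intended endpoint.
2. **Item 6.** Require cooling to be on for all treatment pulses, with a non-zero lower bound taken from the device settings. If uncooled pulses are intended, state the highest fluence at which they are allowed and correct the cooling sentence in the Non-Technical Summary.

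The cost is a few test pulses per subject, slightly less operator latitude, one reworded item and one table entry. Treatment speed need not suffer. At the maximum 2 Hz there are 1000 / 2 = 500 ms per pulse. The longest permitted spray plus the longest pulse takes 50 + 50 = 100 ms, which leaves 400 ms for any delay between them (the delay is not given in the protocol).

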- 1. Subjects will return to the study site for a one (1), three (3) and (6) month follow-up visits after the laser treatment.
- 2. The treatment areas will be photographed.
- 3. Tape measurements and weight will be recorded.
- 4. Ultrasound and skin elasticity measurements will be done if they were done at baseline.
- 5. A clinical evaluation of purpura, edema, erythema, hyperpigmentation, hypopigmentation, blistering and scarring will be assessed by the investigator using the following scale:

0 = absence

1 = mild

2 = moderate

3 = severe

- 6. At the follow-ups the subjects will be asked to evaluate their satisfaction with the treatments. They will be asked to complete the questions below. The first question will ask the subject to rate each treatment procedure using the following scale:
 - 1 = Not Satisfied
 - 2 = Little Satisfaction
 - 3 = Somewhat Satisfied
 - 4 = Satisfied
 - 5 = Very Satisfied
- 7. The subject will also be asked to rate the overall improvement in the appearance of their treated skin using the following scale:
 - 1 = No improvement
 - 2 = Little improvement
 - 3 = Moderate improvement
 - 4 = Significant improvement
 - 5 =Complete improvement
- 8. The subject will have the option to receive an additional treatment on the control side if the treatment results in asymmetric improvement of cellulite. They may have this option starting at the final follow-up.

SECTION 4: SUBJECTS (PERSONS/CHARTS/RECORDS/SPECIMENS)

A. Number of Subjects (Charts/Records/Specimens)

- Indicate the maximum number of subjects to be consented on this UCI protocol.
 - Include projected screen failures and early withdrawals.
 - For Mail/Internet surveys include the number of people directly solicited.
 - If the study involves use of existing charts, records, specimens, specify the maximum number that will be reviewed to compile the data or the sample population necessary to address the research question.

40

- 2. Of the maximum number of subjects listed above, indicate the **target sample size** for the study.
 - The target sample size is the number of subjects expected to complete the study or the number necessary to address the research question.
 - If the study only involves use of existing records, charts, specimens, specify the target number needed to address the research question.

24

Explain how the study sample size was determined (e.g., power analysis; review of related literature).

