This is a pilot trial; therefore there is no basis for the sample size needed to determine a significant difference.

- 4. For multi-center research, indicate the overall sample size for the entire project (across all sites).
- [x] Not applicable This study is not a multi-center study.

B. Inclusion and Exclusion Criteria

1. Describe the **characteristics** of the proposed subject population (age, gender, health status, language, etc.)

Male or female \geq 18 years of age.

- 2. Provide the inclusion and/or exclusion criteria for the proposed subject population, as applicable.
- [] Not applicable This is not a clinical investigation and/or characteristics of the population sufficiently describe the proposed subject population.

Inclusion Criteria

- 1. Male or female \geq 18 years of age
- 2. Cellulite on the arm, knee, thigh or abdomen at stage 2 3 of cellulite per Nurnberger-Muller scale.
- 3. Subject is not overweight per B.M.I. criteria (B.M.I < 27).
- 4. Subject has Fitzpatrick skin phototype I-IV.
- 5. Subject is willing to participate in study and adhere to follow-up schedule.
- 6. Subject has signed the Informed Consent Form.

Exclusion Criteria

- 1. Subjects that have cellulite at stage 0-1 per Nurnberger-Muller Scale (the doctor will determine this)
- 2. Subjects that have had liposuction or other surgical procedures (including Mesotherapy) to remove fat on the proposed treatment area during the past year.
- 3. Subject has severe cellulite with referral to pain and/or tenderness on the area to be treated (Texture Scale: edematous).
- 4. Subject is overweight (BMI \geq 27).
- 5. Subject has known photosensitivity or history of ingesting medications known to induce. photosensitivity in the previous 3 months.
- 6. Subject has a personal or family history of keloid formation or of scarring.
- 7. Subject is pregnant or lactating.
- 8. Subject has a history of uncontrolled diabetes, and/or who requires medication which may interfere with the study.
- 9. Subjects with a known history of neuropathy.
- 10. Subjects with a known history of a coagulopathy.
- 11. Subject is unable or unwilling to comply with the study requirements.
- 12. Subject has a pacemaker or metallic implants.
- 13. Subject has Fitzpatrick skin type V and VI.
- 14. Subject is mentally incompetent or a prisoner.

3. If inclusion/exclusion is based on age, gender, pregnancy/childbearing potential, or race/ethnicity, provide a scientific rationale.

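### The safety signs have no scheduled pre-treatment grade and no specified control-side grade, so existing pigment change may be misattributed to the laser, or real change discounted

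*Protocol*

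**What the plan says.** Section 1 makes safety part of the study objective and names the measure: "Safety will be assessed by clinical evaluation of purpura, edema, erythema, hyperpigmentation, hypopigmentation, blistering and scarring". The Long Term Follow-Up Procedure, item 5, repeats it: "A clinical evaluation of purpura, edema, erythema, hyperpigmentation, hypopigmentation, blistering and scarring will be assessed by the investigator using the following scale". In both places the scale is 0 = absence, 1 = mild, 2 = moderate, 3 = severe. Neither place names a body side or refers to change.

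In the Treatment Procedure schedule, the row "Assessments of side effects" is marked at Tx 1, 1 month and 3 months, and is blank at Pre-Tx. The Pre-Treatment Procedure has 11 steps. One is an eligibility check: "The subject will undergo a standard exam to determine if they meet the study criteria". Another grades cellulite on two scales. None grades pigment or scarring.

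On the untreated side, the design description says: "The contra-lateral side will not be treated and will serve as a control". Section 1 bases efficacy on the difference between the two sides.

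Three other provisions bear on the point:
- Pre-Treatment Procedure, item 8, on the baseline photographs: "Photographs will be of the treated and control areas".
- The design description has the site re-located at each visit "by viewing the baseline photograph and using landmarks such as freckles and birthmarks".
- Exclusion criterion 6 in Section 4.B: "Subject has a personal or family history of keloid formation or of scarring".

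**The concern.** Purpura, blistering and acute redness or swelling are unlikely to have been on the skin beforehand. Hyperpigmentation and hypopigmentation are different, because they can exist before treatment and persist through follow-up. A scale that scores presence and severity gives an old mark and a laser-induced mark the same grade. A recorded baseline grade, or a grade on untreated skin of the same subject, would separate them. The protocol schedules the first nowhere and specifies the second nowhere.

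This matters here for three reasons. Pigment change is a safety question the protocol itself raises: Section 4.B cites dyspigmentation when explaining its skin-type restriction, and Section 7.B says skin changes may be permanent. The design description says the laser is also cleared for treating benign pigmented lesions, so an existing mark could fade as well as darken, and a single follow-up grade shows neither direction. The trial is open label and the investigator does the grading. Whether a mark is old is therefore an unblinded judgement, and the error can go either way: a false event, or a real one set aside.

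**Working it through.** The protocol gives no figure on this point, so there is none to reproduce. The check is first of the text, then an illustration of size.

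**Text check**

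1. *Does the scale measure change?* No. Its lowest category is absence of the sign, not absence of change, in both Section 1 and the follow-up procedure.
2. *Is there a baseline grade?* None is scheduled. The Pre-Tx cell is blank and none of the 11 pre-treatment steps covers these signs. The Tx 1 mark does not say whether grading comes before or after the laser. The list of immediate post-treatment steps runs from 1 to 3 in the available copy, so a step may be missing there. The Tx 1 grade therefore cannot be called post-laser with certainty, nor can it be relied on as a baseline.
3. *Is the control side graded?* No text says that it is, and none says that it is not.
4. *Is a side effect defined as new or worsened?* No such rule appears.
5. *Do the photographs fill the gap?* In part. They record both sides before treatment under standardised conditions. The instruction to view the baseline photograph, however, serves consistent photography, ultrasound and measurement. Nothing links it to the 0-3 grades.
6. *Do the eligibility criteria fill the gap?* Largely for scarring, through criterion 6. Not for pigment: no criterion excludes existing pigment change, and the protocol expects freckles and birthmarks at the sites, since it uses them as landmarks.

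**Illustration of size**

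Inputs: n = 24, the target sample size in Section 4.A; p = the proportion of subjects with a gradable mark in the treated area before treatment. The documents give no value for p, so 2% to 20% is an assumed range. Subjects are taken as independent.

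Expected number = n × p. Chance of at least one = 1 − (1 − p)^n.

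| p (assumed) | 24 × p | 1 − (1 − p)^24 |
|---|---|---|
| 2% | 0.48, about 0.5 | 1 − 0.98^24 = 0.384 |
| 5% | 1.2 | 1 − 0.95^24 = 0.708 |
| 10% | 2.4 | 1 − 0.90^24 = 0.920 |
| 20% | 4.8 | 1 − 0.80^24 = 0.995 |

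The table counts subjects who have a mark beforehand. It equals the number of falsely attributed events only if every such mark is graded at least 1 and the baseline photograph is never consulted, so each figure is an upper bound on false attribution. It does not measure the opposite error, a real change dismissed as old.

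**The case against.** The strongest case against the point is that the safeguards already exist. Standardised photographs of both sides are taken before treatment, the baseline photograph is viewed at each visit, and the marks in question are the landmarks used to find the site. An investigator assessing side effects of a laser would not naturally score a long-standing birthmark as one. Criterion 6 removes most of the scarring problem. The definition of a treatment-emergent event is commonly left to an SAP or case report form, and neither is shown. Control-side grading of purpura or blistering would add little in a pilot of 24.

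Much of this stands, and it rules out several stronger readings:
- A reader might infer that old marks will be counted as laser side effects. The protocol has no such counting rule; it leaves the matter to judgement.
- A reader might infer that old and new marks cannot be told apart, or that worsening cannot be seen. The photographs contradict this.
- A reader might infer that the control side is excluded from safety assessment, or that grading is only post-laser. The first is silence in the text, and the timing at Tx 1 is not stated.
- A reader might give scarring equal weight with pigment. Criterion 6 does not support that.

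One part of the defence fails. An SAP can define new or worsened, but it cannot supply a live baseline or control-side grade that was never taken. What is graded, when and on which side is data collection, and the protocol fixes that. Later grading from photographs is possible, but it is a different assessment and is not planned.

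**Conclusion.** The point holds as a modest weakness in how safety data are collected, mainly for hyper- and hypopigmentation and to a much smaller extent for scarring. With no scheduled Pre-Tx grade, no specified control-side grade, an absolute scale and no new-or-worsened rule, attribution of these signs rests on the unblinded investigator's view of what was there before. The baseline photographs lower the risk without removing it.

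The size cannot be fixed from the documents. Across the assumed range it runs from about half a subject to about five of 24, as a ceiling on false attribution. The conclusion does not depend on any one value in that range. It rests on the schedule and the procedure lists, and on the fact that the missing grades cannot be recovered afterwards as live assessments.

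**What to change.** Add a Pre-Tx mark to the side-effect row of the schedule. At Pre-Tx and every follow-up visit, grade hyperpigmentation, hypopigmentation and scarring 0-3 on both the treated and the control side, with the baseline photograph at hand. State that grades which are new or worsened from the Pre-Tx grade will be reported, treated versus control. The acute signs can stay as they are. State also whether the Tx 1 assessment is made before or after the laser.

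The cost is a few extra minutes per visit for the investigator already present and some added form fields. No new visit or equipment is needed.
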